7.2.2. Subject Electronic Diary

The subject will be asked to monitor and record local reactions, systemic events, fever, and antipyretic/pain medication used to treat symptoms, each evening for 14 days following vaccination (Day 1 through Day 14, where Day 1 is the day of vaccination) on a system that uses a personal digital assistant (PDA) or other technology. This system, hereafter referred to as the subject's e-diary, allows recording of these assessments only within a fixed time window, thus providing the accurate representation of the subject's experience at that time. Data on local reactions, systemic events, fever, and antipyretic/pain medication used to treat symptoms reported on the e-diary will be transferred electronically to the e-diary vendor, where they will be available for review by investigators, their appropriately qualified designees, and sponsor staff at all times via an internet-based portal. At intervals agreed to by the vendor and Pfizer, these data will be transferred electronically to Pfizer for analysis and reporting.

These data do not need to be reported by the investigator in the CRF. However, if a subject withdraws because of prompted events reported in the e-diary, the event(s) should be recorded on the AE page of the CRF, regardless of whether the investigator considers the event(s) to be clinically significant.

Investigators (or appropriately qualified designees) are required to review the e-diary data online at frequent intervals (daily is optimal) to evaluate subject compliance and as part of the ongoing safety review (see Stopping Rules in [Section 7.2.1](#)).

The investigator or designee must contact the subject in order to obtain stop dates for any reactions ongoing on the last day that the e-diary was completed. The stop dates should be entered in the CRF at Visit 2.

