- a. The variable will be derived for any local reaction (any redness, swelling, pain at the injection site) and also for any severe local reaction within Day 1 to Day 14 following vaccination.

Duration (From First Day to Last Day Reported)

The duration of each local reaction will be calculated as the number of days from the start of the first reported reaction to the resolution of the last reported reaction, inclusive. Days with redness or swelling with diameter <2.5 cm will be excluded. Resolution is the last day on which the reaction is recorded in the e-diary if the reaction lasted 14 days or less, or the date the reaction ended if it continued beyond Day 14 (the latter will be collected on the CRF). If there is no known date when the reaction ended, then duration will be missing (unknown). Subjects with no reported reaction have no duration because it is not applicable.

Duration of reactions ≥ 21 measuring device units will also be compiled.

Duration (Total Days Reported)

The duration (total days) of each local reaction will be calculated as the number of days with the reported reaction, including days after Day 14 (if any). Days with redness or swelling with diameter <2.5 cm will be excluded.

If there is no known date when the reaction ended, then duration (total days) will be missing (unknown). Subjects with no reported reaction have no duration because it is not applicable.

Total days of reactions ≥ 21 measuring device units will also be compiled.

Onset

The onset day of each local reaction and any local reaction will be derived. Days with redness or swelling with diameter < 2.5 cm will be excluded.

For the onset day of each local reaction, if subjects report severity change of the local reaction, only the first day of reporting that specific local reaction will be counted.

For the onset day of any local reaction, the first day of reporting any severity of any local reaction will be counted.

CCI

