Oral temperature will be collected in the evening daily for 14 days following vaccination (Days 1 to 14, where Day 1 is the day of vaccination) and at any time during the 14 days that fever is suspected. Fever is defined as an oral temperature of $\geq 100.4^{\circ}\text{F}$ ($\geq 38.0^{\circ}\text{C}$). The highest temperature for each day will be recorded in the e-diary. In the event of a fever on Day 14, temperature will be collected daily until fever has resolved (1 day of temperature less than 100.4°F [38.0°C] in order to collect a stop date in the CRF). Temperature will be measured and recorded to 1 decimal place and then grouped into ranges for the analysis according to Table 5 below:

Table 5. Ranges for Fever

100.4°F to 101.1°F (38.0°C to 38.4°C)
101.2°F to 102.0°F (38.5°C to 38.9°C)
102.1°F to 104.0°F (39.0°C to 40.0°C)
>104.0°F (>40.0°C)

Maximum severity for fever over Days 1 to 14 will be defined as $>104.0^{\circ}\text{F}$ ($>40.0^{\circ}\text{C}$).

For each systemic event, the following endpoints and variables will be derived for analyses following the same rules as for local reactions in [Section 6.1.1](#), where applicable:

- Maximum severity of each systemic event or fever on any day (Day 1 to Day 14);
- Presence (yes or no) of each systemic event or fever on each day (Day 1 to Day 14);

- Presence (yes or no) of each systemic event or fever on any day (Day 1 to Day 14);
- Presence (yes or no) of any systemic event or fever on any day (Day 1 to Day 14);
- Presence (yes or no) of each severe (Grade 3 as defined in [Table 4](#)) systemic event (this will include fever $>104.0^{\circ}\text{F}$ [$>40.0^{\circ}\text{C}$]) on each day and on any day (Day 1 to Day 14);
- Duration of each systemic event or fever (duration will be calculated both from the first to the last day and also as total days with the indicated event);
- Onset day of each systemic event or fever;

CCI

For the purposes of deriving the variable “any systemic event” on any day (Day 1 to Day 14) or each day, the systemic events headache, fatigue, muscle pain, and joint pain will be included, and fever will be included as one of the possible systemic events.

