8. STATISTICAL METHODOLOGY AND STATISTICAL ANALYSES

8.1. Statistical Methods

All analyses will be descriptive. Unless otherwise explicitly stated, descriptive statistics for continuous variables are n, mean, median, standard deviation, minimum, and maximum. Descriptive statistics for categorical variables are the percentage (%) and the numerator (n) and the denominator (N) used in the percentage calculation.

No formal hypothesis testing will be performed.

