8.2.1.1. Local Reactions, Systemic Events, and Fever

The derived endpoints for each local reaction ([Section 6.1.1](#)), systemic event, and fever ([Section 6.1.2](#)) during Day 1 to Day 14 following vaccination, where Day 1 is the day of vaccination, will be summarized as the proportions of subjects with the associated 95% Clopper-Pearson CIs ([Section 8.1.1](#)) and descriptive statistics for each vaccine group.

The presence and maximum severity of each event and any event within 14 days following vaccination will be summarized by proportions of subjects with the associated 95% Clopper-Pearson CIs and descriptive statistics for each vaccine group.

Another set of summaries for the presence of each event and any event, and for events that are severe in grade, on each day and any day of Day 1 to Day 14 following vaccination will also be provided by day for each vaccine group in the proportions of subjects with the associated 95% Clopper-Pearson CIs, by each event and any event.

Figures of the bar charts plotting the proportions of subjects for each derived event will be plotted by day for each vaccine group. The bar charts will be divided into severity subgroups to highlight the proportions of subjects by severity.

For redness and swelling, the maximum reported diameters in centimeters (cm) will be summarized according to the severity categories specified in [Table 1](#), for each vaccine group.

For each local reaction and systemic event, including fever, the duration of each event will be summarized using descriptive statistics for each vaccine group. Duration will be calculated as the last day minus the first day + 1, including any intervening days without the indicated event. Only subjects actually reporting the event will be included in the summary statistics. Bar charts plotting the proportions of each event each day will be inspected for possible skips, ie, the event tends to appear, disappear, then reappear. If skips are observed, then duration (total days) will be calculated as the total number of days on which the subject experienced the indicated event.

Duration (from the first day to the last day reported) will be obtained for every event. Duration (total days) will also be obtained for every event.

The onset day of each local reaction and systemic event, including fever, will be summarized using descriptive statistics for each vaccine group.

CCI

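### Prompted reactions with no known end date drop out of the duration summaries, which tends to understate the mean and sometimes the maximum duration

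*SAP*

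**What the plan says.** SAP 6.1.1 defines two durations for each local reaction. For the span from first to last day: "If there is no known date when the reaction ended, then duration will be missing (unknown". For the count of days with the reaction: "If there is no known date when the reaction ended, then duration (total days) will be missing (unknown". SAP 6.1.2 derives the systemic-event and fever variables "following the same rules as for local reactions in" Section 6.1.1, where applicable.

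A reaction that outlasts the diary is not lost for that reason alone. Its end is taken as "the date the reaction ended if it continued beyond Day 14 (the latter will be collected on the CRF". Under Protocol 7.2.2 the investigator or designee "must contact the subject in order to obtain stop dates for any reactions ongoing on the last day" of diary completion, and "The stop dates should be entered in the CRF at Visit 2". Fever present on Day 14 is followed with daily temperatures until it resolves (Protocol 7.2.3.3, SAP 6.1.2).

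On reporting, SAP 8.2.1.1 says "Only subjects actually reporting the event will be included in the summary statistics", and under SAP 8.1 the "descriptive statistics for continuous variables are n, mean, median, standard deviation, minimum, and maximum". SAP 7 deals with missing prompted-event data by referring back to 6.1.1 and 6.1.2. The visible text contains no censored-data summary, no sensitivity analysis for duration, and no count of events with an unknown end.

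**The concern.** When no end date is known, the onset day and the last day on which the reaction was recorded are still known. The duration is right-censored, not unknown. Setting it to missing discards a lower bound, and the chance of being discarded rises with length: a reaction that resolves within a completed diary always has an end date, while one unresolved at Visit 2 has no stop date to enter.

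No later step visibly recovers these values. The Month 6 and Month 12 contacts (Protocol 6.1.4, 6.2.3, 6.2.4) name follow-up of AEs, SAEs and NDCMCs, not diary events, and the later safety analyses in SAP 3 start from the 1-month visit. The by-day tables in SAP 8.2.1.1 stop at Day 14, and the listing there covers severe reactions, fever above 104°F and unscheduled assessments. A mild or moderate reaction still present at one month could therefore show only as a gap between the n in the duration table and the number reporting the event.

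At stake is how well the study describes persistence. Duration is a specified variable for every prompted event, in a first-in-human study whose primary objective is to describe safety.

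**Working it through.** The plan states no expected duration and no rate of unknown end dates, so there is no figure of its own to reproduce. The check has three steps.

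**1. What minimum is known for a dropped event?** Minimum = last day known present − onset day + 1. Vaccination is Day 1 and Visit 2 falls 28 to 35 days later, that is, on study Days 29 to 36.
- Present at Visit 2, onset Day 1: 29 to 36 days.
- Present at Visit 2, onset Day 2: 28 to 35 days.
- Present at Visit 2, onset Day 14: 16 to 23 days.
- Known present only up to Day 14: 14 days for onset Day 1, 8 for Day 7, 2 for Day 13, 1 for Day 14.

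Events unresolved at Visit 2 are therefore long. Late-onset events with no information after Day 14 have a short minimum.

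**2. Effect on the mean.** Assumptions: 60 subjects report the event, k have no known end, and the other 60 − k average 3.0 days. The SAP rule reports 3.0 whatever k is. Including the k events at minimum L gives

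mean = ((60 − k) × 3.0 + k × L) / 60.

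| k | L = 28 | L = 16 | L = 2 | L = 1 |
|---|---|---|---|---|
| 1 | 3.42 | 3.22 | 2.98 | 2.97 |
| 3 | 4.25 | 3.65 | 2.95 | 2.90 |
| 5 | 5.08 | 4.08 | 2.92 | 2.83 |

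For example, k = 5 and L = 28 gives (55 × 3.0 + 5 × 28)/60 = 305/60 = 5.08. The slight falls at L = 1 or 2 arise because a lower bound is being averaged. They do not show that those reactions were short.

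**3. Median and maximum.** These need a distribution. Known durations were set at evenly spaced quantiles of a geometric distribution, ceil(ln(1 − q)/ln(1 − 1/μ)), with μ = 2.5 or 4 days and a cap of 14. With 100 reporters, μ = 2.5 and 3 unknown ends:

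| Handling | Mean | Median | Maximum |
|---|---|---|---|
| SAP rule (dropped) | 2.52 | 2 | 11 |
| Included at 14 days | 2.86 | 2 | 14 |
| Included at 29 days | 3.31 | 2 | 29 |

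Across 1 to 10 unknown ends among 100 reporters, bounds of 14 to 36 days and both values of μ, the mean rises by 0.10 to 3.35 days and the median does not move. With 15 reporters (nearer Stage 1) and one unknown end, the mean rises by 0.68 to 2.24 days, again with the median unchanged.

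The maximum is not always understated. If one resolved 25-day reaction is kept and the 3 unknown ends enter at 14 days, the mean goes from 2.73 to 3.07 and the maximum stays at 25.

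**The case against.** A reader might infer that the plan removes the longest-lasting reactions, so that mean, median and maximum are all biased short. The documents do not support that.

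- A reaction that ends on Day 25 with a CRF stop date stays in both measures. Only events whose end is never obtained are dropped.
- Contact to obtain stop dates is mandatory, and Visit 2 gives a second opportunity, so the number dropped may be small. No rate is given in either direction.
- An unknown end does not prove a long reaction. Dropout, a diary that stops early or poor recall can also cause it.
- The median was unchanged in every scenario with a bound of 14 days or more, and the maximum moves only if a dropped event outlasts the longest resolved one.
- Fever has its own follow-up, so the carry-over matters mainly for headache, fatigue, muscle pain and joint pain.
- The primary endpoints are proportions and do not use duration. No group comparison is tested, n is reported with each summary, and persistence through Day 14 is visible in the by-day tables.

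All of this stands and limits the point. It does not remove it: for the events that do drop out, the plan discards a known lower bound and does not commit to saying how many there were.

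**Conclusion.** The concern holds in limited form. Following SAP 6.1.1 as written tends to understate mean duration, and sometimes the maximum, because reactions unresolved when last assessed are treated as having no information.

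Under the assumptions of 60 reporters and 3.0 days among resolved cases, the understatement runs from about 0.2 days (one event, 16-day minimum) to about 2.1 days (five events, 28-day minimum), and is about zero if the dropped events have minimums of 1 or 2 days. These inputs are illustrative. The real size rests on the unstated rate of unknown end dates and on how long those reactions had already lasted. The issue is one of descriptive completeness and does not threaten the primary analyses.

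**What to change.** In SAP 6.1.1, and so in 6.1.2 where applicable, replace the missing-value rule with a lower-bound (right-censored) duration:

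- **First-to-last duration:** last day the event was known to be present (last positive e-diary day, or Visit 2 if recorded as ongoing) − onset day + 1, flagged as censored.
- **Total days:** the number of days on which the event was recorded as present, flagged as a minimum. Censoring at a calendar date does not define a value here, because this measure skips event-free days.
- **Reporting, per event and vaccine group:** the number and percentage with no known end date and their minimum durations; a mean that includes them at their minimum, beside the planned mean; and the maximum as ≥ x days where the longest value is censored.

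A Kaplan-Meier median for first-to-last duration is an optional supplement. It assumes non-informative censoring, which is doubtful if subjects stop the diary while symptomatic.

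The cost is SAP wording and light programming. One item needs confirming: for diary events the visit procedures describe recording stop dates, while the wording about confirming that an event continues is attached to AEs, SAEs and NDCMCs. If the CRF does not record a diary event as ongoing at Visit 2, the bound falls back to the last positive diary day. The resulting figures would be at most slightly less favourable.

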6.1.2. Systemic Events and Fever

Within each study stage, the systemic events assessed and recorded in the e-diary are headache, fatigue, muscle pain, and joint pain, from Day 1 to Day 14 following vaccination, where Day 1 is the day of vaccination.

For each systemic event, the maximum severity grade of the event based on the severity grading scale in [Table 4](#) will be derived for the e-diary collection period (Day 1 to Day 14, where Day 1 is the day of vaccination) as follows:

- = missing, if all values are missing for Day 1 to Day 14;
- = 0, if the subject reports all reactions as “no” or a combination of missing and “no” for all Days 1 to 14;
- = highest grade (maximum severity) within 14 days of vaccination (Day 1 to Day 14) among severity grades where the answer is not “no” for at least 1 day during Days 1 to 14.

The symptoms of systemic events will be assessed by the subject as mild, moderate, or severe according to the severity grading scales of each systemic event in Table 4 below. Grade 4 will not be collected in the e-diary but will be collected as an AE on the CRF. Grade 4 will not be analyzed as part of systemic events.

Table 4. Grading Scales for Systemic Events

	Mild Grade 1	Moderate Grade 2	Severe Grade 3	Grade 4
Fatigue (tiredness)	Does not interfere with activity	Some interference with activity	Prevents daily routine activity	Emergency room visit or hospitalization
Headache	Does not interfere with activity	Some interference with activity	Prevents daily routine activity	Emergency room visit or hospitalization
Muscle pain	Does not interfere with activity	Some interference with activity	Prevents daily routine activity	Emergency room visit or hospitalization
Joint pain	Does not interfere with activity	Some interference with activity	Prevents daily routine activity	Emergency room visit or hospitalization

Abbreviation: e-diary = electronic diary.

Oral temperature will be collected in the evening daily for 14 days following vaccination (Days 1 to 14, where Day 1 is the day of vaccination) and at any time during the 14 days that fever is suspected. Fever is defined as an oral temperature of $\geq 100.4^{\circ}\text{F}$ ($\geq 38.0^{\circ}\text{C}$). The highest temperature for each day will be recorded in the e-diary. In the event of a fever on Day 14, temperature will be collected daily until fever has resolved (1 day of temperature less than 100.4°F [38.0°C] in order to collect a stop date in the CRF). Temperature will be measured and recorded to 1 decimal place and then grouped into ranges for the analysis according to Table 5 below:

Table 5. Ranges for Fever

100.4°F to 101.1°F (38.0°C to 38.4°C)
101.2°F to 102.0°F (38.5°C to 38.9°C)
102.1°F to 104.0°F (39.0°C to 40.0°C)
>104.0°F (>40.0°C)

Maximum severity for fever over Days 1 to 14 will be defined as $>104.0^{\circ}\text{F}$ ($>40.0^{\circ}\text{C}$).

For each systemic event, the following endpoints and variables will be derived for analyses following the same rules as for local reactions in [Section 6.1.1](#), where applicable:

- Maximum severity of each systemic event or fever on any day (Day 1 to Day 14);
- Presence (yes or no) of each systemic event or fever on each day (Day 1 to Day 14);

- Presence (yes or no) of each systemic event or fever on any day (Day 1 to Day 14);
- Presence (yes or no) of any systemic event or fever on any day (Day 1 to Day 14);
- Presence (yes or no) of each severe (Grade 3 as defined in [Table 4](#)) systemic event (this will include fever $>104.0^{\circ}\text{F}$ [$>40.0^{\circ}\text{C}$]) on each day and on any day (Day 1 to Day 14);
- Duration of each systemic event or fever (duration will be calculated both from the first to the last day and also as total days with the indicated event);
- Onset day of each systemic event or fever;

CCI

For the purposes of deriving the variable “any systemic event” on any day (Day 1 to Day 14) or each day, the systemic events headache, fatigue, muscle pain, and joint pain will be included, and fever will be included as one of the possible systemic events.

6.1.3. Use of Antipyretic/Pain Medication

Within each study stage, the use of antipyretic/pain medication to treat fever or pain is also recorded in the e-diary from Day 1 to Day 14 following vaccination, where Day 1 is the day of vaccination.

For the use of antipyretic/pain medication, the following endpoints and variables will be derived for analyses following the same rules as for local reactions in [Section 6.1.1](#), where applicable:

- Presence (yes or no) of use of antipyretic/pain medication on each day (Day 1 to Day 14);
- Presence (yes or no) of use of antipyretic/pain medication on any day (Day 1 to Day 14);
- Duration of use of antipyretic/pain medication;
- Onset day of use of antipyretic/pain medication.

The use of antipyretic/pain medication will be summarized and included in the systemic event summary tables, but will not be considered a systemic event.

[figure not shown]
CCI

[figure not shown]

6.1.4. Adverse Events

AEs will be captured and reported in accordance with Pfizer reporting standards.

AEs will be assessed up to 1 month after vaccination within each of Stage 1 and Stage 2, separately. SAEs and NDCMCs will be assessed throughout the study and collected by a telephone call at 6 months after vaccination within each of Stage 1 and Stage 2, and collected during a clinic visit at 12 months after vaccination for Stage 2 only.

6.2. Immunogenicity Endpoints

The immunogenicity endpoints are the secondary and exploratory endpoints of the study.

6.2.1. Secondary Endpoints

- Pneumococcal serotype-specific opsonophagocytic activity (OPA) geometric mean titers (GMTs) measured at 1 month after vaccination, for each study stage.
- Pneumococcal serotype-specific OPA geometric mean fold rises (GMFRs) measured from before vaccination to 1 month after vaccination, for each study stage.

CCI

The figure consists of a large black rectangular redaction box covering the bottom portion of the page content. Above this redaction, the acronym 'CCI' is printed in red.

CCI

6.2.3. Immunogenicity Variables

Immunogenicity variables collected for this study are the results of assays performed on the blood samples collected. The results of these assays are CCI antibody titers (OPA) C C

OPA Titer

OPA titers for the complementary 7 pneumococcal serotypes (8, 10A, 11A, 12F, 15B, 22F, and 33F) will be determined in all subjects for each blood sample at Day 1 prior to vaccination (baseline) and 1 month after vaccination (Stage 1 and Stage 2). CCI

CCI

CCI

CCI

Age Group	Percentage of CCI
18-24	~10%
25-34	~20%
35-44	~30%
45-54	~40%
55-64	~50%
65-74	~65%
75+	~95%

Term	Percentage
GMOs	85%
Organic	80%
Natural	75%
Artificial	65%
Organic	60%
Natural	55%
Artificial	50%
Organic	45%
Natural	40%
Artificial	35%
Organic	30%
Natural	25%
Artificial	20%

CCI

